Feasibility of Teleyoga for Treatment of Lyme Disease

Study Protocol and Statistical Analysis Plan

NCT #: 04867473

June 21, 2023

Background

Lyme Disease (LD) is a debilitating condition, which infects an estimated 300,000 people each year and is associated with high personal and societal costs (1). Lyme Disease is associated with many symptom sequelae, including fatigue, joint and muscle pain, and cognitive difficulties, which impact daily activities (5). In later phases, untreated LD can lead to arthritis and arthralgias, cardiac complications, and even death. Though most early phase LD patients are successfully treated with one course of antibiotics, a minority (10-20%) of those successfully treated continue to experience persistent symptoms of fatigue, depression, musculoskeletal pain, and cognitive complaints, called Post Treatment Lyme Disease Syndrome (PTLDS) (2). The efficacy of a repeat course of antibiotics has not been supported for PTLDS; rather, typical recommended treatments are cognitive behavior therapy (CBT), antidepressants, and low-impact aerobic exercise. The efficacy of these interventions appears to be limited. Consequently, an adjunct treatment to medication interventions for LD that is non-invasive, has a low side-effect profile, and is relatively easy to implement at home could address these primary complaints. Although studies have shown yoga improves symptoms of chronic pain, cognition, sleep, and mood (3), no clinical trial has examined yoga for LD. However, yoga may be valuable for treating musculoskeletal pain in LD for several reasons: First, LD patients often report reductions in daily movement and exercise (5), which yoga could address, promoting increased physical strength and stamina. Second, musculoskeletal pain and LD share a pathological overlap of emotional problems and poor cognition, both of which respond positively to yoga. Additionally, the neuropsychological burden often reported by LD sufferers as “brain fog” has not been well established, with some studies demonstrating difficulties in memory, verbal fluency, and/or executive functioning and others finding subclinical changes or failing to replicate these findings (5). To establish the cognitive status of patients reporting LD symptoms, we intend to identify and track changes in measures of memory, verbal fluency, and executive functioning.

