We will adapt the yoga protocol from the parent award. The protocol is 12 weeks in duration, 1 class/week, class length of 75 minutes, with additional homework 15-20 mins on 5 non-class days/week. The protocol uses seated/standing/supine yoga postures, breathing, and meditation, and contains standard modifications in cases of limited mobility. Participants will also receive a homework manual describing simple and safe exercises to practice for homework. The adapted protocol would be 10 weeks in duration, to allow for recruitment intervals, but would otherwise adhere to the active award protocol.

Recruitment: For each 3-month interval we will recruit N=5 LD and PTLDS patients.

We anticipate recruitment will be via local hospitals, including Stanford, and the Johns Hopkins Lyme Disease Research Center, a research center with an online recruitment resource and ongoing clinical trials.

Baseline: Participants will complete study measures at the study site (see Assessment Materials below). We will record their phone number, physical location, and an emergency contact, which will be confirmed at each teleyoga session.

Week 1: Participants will visit the study center and will be issued an Apple iPad. They will also receive a yoga mat, yoga strap, and yoga blocks. Since the goal is to address the technical feasibility of teleyoga, this session will focus on anticipated technical issues, such as charging the iPad, connecting the iPad to home Wi-Fi, using the volume buttons, using the case as a stand, at-home lighting requirements, etc. We will also provide these instructions in a booklet. These initial steps can be performed remotely if participants cannot visit the study center.

Weeks 2-8: Study staff will call caregivers one day prior to instruction and remind them to charge their iPad and join the upcoming session. The yoga instructor providing instruction will be located at home equipped with standard audiovisual apparatus (i.e., screen size 56" x 32").

Post-Treatment: Participants will visit the study site individually to complete study measures (see "Assessment Materials" section) and provide feedback.

Statistical Plan and Data Analysis

Primary analyses will be conducted focusing on treatment satisfaction, provider suggestions, retention and adherence. Due to the very small sample size (N=15) the main analytic strategy will be descriptive statistics. We will carefully examine score distributions and

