will focus on cases with negative responses for treatment satisfaction. We aim to reach at least 2 on the 5-point MDTSM scale (i.e., satisfaction is neutral or positive) for all items. For retention, we aim to retain at least 65% of all participants in the study during the 10 weeks of treatment. We expect treatment attendance to be $\geq 65\%$ for the 10 treatment sessions. For feasibility of treatment fidelity we will aim for $\geq 95\%$ of treatment components. For the outcomes that will be measured repeatedly (i.e., both at baseline and post-treatment), we will estimate how they change over time (pre to post). These results will provide preliminary data on target engagement and therefore will inform and shape the future trial in terms of elucidating the mechanism of action. For all analyses regarding changes in outcomes, we will first employ simple paired t-test (pre vs. post) given the correlation between pre and post measures. In all statistical analyses, we will focus on collecting preliminary data on clinical significance (i.e., effect size) instead of making formal inference (i.e., p-value).

Inclusion/Exclusion Criteria

Inclusion Criteria (As determined by):

- Diagnosis of probable Lyme disease
- Has not begun new pain medications or other treatments in the last month
- English literacy
- Wireless internet connection at home

Exclusion Criteria for (As determined by):

- Participation in another concurrent clinical trial
- Back surgery within the last 12 months
- Unstable, coexisting mental illness or psychiatric condition
- Active, current suicidal intent or plan
- Attended or practiced yoga ≥ 1 x in the past 12 months

Informed Consent Process

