Treatment Satisfaction: Assessed using the Multi-Dimensional Treatment Satisfaction Measure (MDTSM). The measure consists of 11 subscales assessing treatment process and outcome attributes. Each subscale has 1-8 items (see Table 5). Each question except the Discomfort subscale is rated on a five-point scale ranging from “not at all (0)” to “very much (4)”. Thus, a score of 2 represents a rating of neutral satisfaction. The instrument was developed for behavioral interventions and is designed to provide a comprehensive set of treatment attributes to consider when evaluating treatments in the context of pilot studies. It is designed to be completed after exposure to an intervention, to point to aspects of treatments that are viewed favorably or unfavorably. The MDTSM is relevant to many types of behavioral interventions and can be tailored to our yoga intervention. The MDTSM subscales demonstrates good internal consistency, reliability, and validity.

PEG: A 3-item pain measure derived from the Brief Pain Inventory and validated in ambulatory care settings. It includes 1 severity item (average pain) and 2 interference items (enjoyment of life and general activity).

SF-36: Health related quality of life-short form (69): Eight scales measuring physical functioning, role limitations due to physical problems, bodily pain, general health perceptions, vitality, social functioning, role limitations due to emotional problems, and mental health.

Cambridge Neuropsychological Test Automated Battery (CANTAB): Cognitive function was measured with the Cambridge Neuropsychological Test Automated Battery (CANTAB) at baseline and end of treatment. Three tests were administered (PAL, SWM and RVP).

| | Data Collection | | | |
|-----------------------------------|-----------------|----------|-----------------|----------------|
| | Screening | Baseline | Yoga (wks 1-12) | Post-treatment |
| Background | | | | |
| Consent Form | × | | | |
| Demographic Questionnaire | × | | | |
| Clinical Questionnaire | × | | | |
| Yoga Medical Clearance Form | × | | | |
| Medical Use | | × | | × |
| Yoga Home Practice Log | | | × | |
| Mental Health | | | | |
| BDI-II | | × | | × |
| Pain/QOL/Physical | | | | |
| PEG | × | × | | × |
| Behavioral & Cognitive | | | | |
| Treatment Satisfaction | | | | × |
| Patient Safety | | | × | × |

| | | | | |
|--------|--|--|---|---|
| SF-36 | | | x | x |
| CanTab | | | x | x |

Table 1. Study Measures and Timetable of Data Collection

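### The pre-post change on the repeated CANTAB tests includes any practice gain, so in a single uncontrolled group it cannot be read as target engagement

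*Combined protocol and SAP*

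**What the plan says.** The CANTAB paragraph under Study Assessments gives the time points, "Cognitive function was measured with the Cambridge Neuropsychological Test Automated Battery (CANTAB) at baseline and end of treatment", and the content, "Three tests were administered (PAL, SWM and RVP"). It says nothing about test versions, practice items, the device or retest norms.

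Cognitive change is an intended readout. The Background states that "we intend to identify and track changes in measures of memory, verbal fluency, and executive functioning". Under Yoga Intervention the programme lasts about ten weeks: "The adapted protocol would be 10 weeks in duration, to allow for recruitment intervals".

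Under Statistical Plan and Data Analysis, every outcome measured at both time points is handled in one way: "we will first employ simple paired t-test (pre vs. post) given the correlation between pre and post measures". On interpretation, "we will focus on collecting preliminary data on clinical significance (i.e., effect size) instead of making formal inference (i.e., p-value". The same section says that these changes give preliminary information on target engagement, and that this will shape the future trial and help to clarify mechanism. There is no control group in this study; the Background defers one to a later, larger trial.

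**The concern.** PAL, SWM and RVP are performance tests. A person can score better the second time simply from having taken the test before. A pain, mood or quality-of-life questionnaire is not open to practice in that way, yet the plan gives both kinds of measure the same paired analysis and the same interpretation.

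With one group, nothing in the described data separates a retest gain from an effect of yoga. Preferring effect sizes to p-values is no protection, because the practice gain sits in the effect size itself. What is at stake is one specific conclusion: that cognitive change shows yoga has engaged its target. That reading would be carried into the next trial although the plan as written cannot support it. The feasibility conclusions are not affected.

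**Working it through.** **1. The plan's own figure.** Hypothesis 1 recruits five patients every three months for nine months: 9 / 3 × 5 = 15, which reproduces N = 15. This is a recruitment target. No alpha, power, SD or effect size is given, so there is no power calculation to check. Retention of 65% means 0.65 × 15 = 9.75, so 10 completers (10/15 = 66.7%; 9/15 would be 60%).

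**2. The bias.** In one group, the expected change on a test is

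expected change = yoga effect + practice effect (+ any other change over time).

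Dividing by the SD of the paired differences gives the paired effect size d_z. A practice effect of *p* SD of change therefore adds *p* to the expected standardised change, whatever the sample size. A larger sample would reduce the noise but not this term.

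**3. An illustration of size.** The documents give no practice figure, so *p* is an assumption, shown over a range that includes zero. The true yoga effect is set to 0, with n = 10 (65% retention) and n = 15 (all complete). The paired t statistic equals d_z × √n. It follows a noncentral t distribution with n − 1 degrees of freedom and noncentrality p × √n.

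- Chance of an observed d_z of at least 0.2: P(t ≥ 0.2√n), where 0.2√n is 0.632 for n = 10 and 0.775 for n = 15.
- Chance of two-sided p < 0.05 in the improving direction: P(t ≥ t₀.₉₇₅,ₙ₋₁).

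| Assumed practice effect p | n = 10: d_z ≥ 0.2 | n = 15: d_z ≥ 0.2 | n = 10: p < 0.05, improving | n = 15: p < 0.05, improving |
|---|---|---|---|---|
| 0 | 27% | 23% | 2.5% | 2.5% |
| 0.2 | 51% | 51% | 8% | 11% |
| 0.3 | 63% | 65% | 13% | 19% |
| 0.5 | 83% | 88% | 29% | 44% |

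These are chances for one test, and three are given. The first two result columns matter most, since the plan will read effect sizes. Random error is also large: the 95% half-width for the mean change is about t₀.₉₇₅ / √n, or 0.72 SD of change for n = 10 and 0.55 for n = 15. A single observed effect is thus very imprecise even without practice; practice shifts what it is centred on.

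**4. When is the first test?** The CANTAB paragraph puts it at baseline. Table 1, as it appears in the extracted text, marks CANTAB under the yoga weeks and post-treatment, with no mark under baseline. The SF-36 row in the same detached fragment of the table has the same pattern, so a column displaced in extraction is a plausible explanation. If the table is right, the interval between tests is shorter than 10 weeks and the first score is not a pre-treatment score. The column is also headed weeks 1-12, against the 10-week programme in the text.

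**The case against.** The strongest reply is that the plan already limits the consequence. The primary analyses are satisfaction, provider suggestions, retention and adherence. The main strategy is descriptive because N = 15. Changes are called preliminary, formal inference is disclaimed and a controlled trial is deferred. No hypothesis predicts cognitive improvement; Hypothesis 2 is about cognitive status. Practice is one of several threats to any uncontrolled pre-post comparison. The plan speaks of shaping the next trial and does not say that CANTAB change will size it. All of this stands and keeps the weight low. It does not answer the point, because the same section still assigns the changes a use, target engagement, that practice undermines.

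A second reply is that the document is silent on versions and practice runs, and silence is not absence. That also stands: none is described, and no more can be said.

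Third, the CANTAB paragraph is in the past tense, which may mean that testing was finished by the document date of 21 June 2023. If so, test versions can no longer be changed, but the reporting wording can.

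A reader might infer three stronger points that the documents do not support:

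- **Carry-over from iPad use.** Under Week 1, "Participants will visit the study center and will be issued an Apple iPad", and it is used for the classes. No text says that CANTAB runs on an iPad or any tablet, so this is conjecture.
- **An unfamiliar first test also favours Hypothesis 2, so both errors suit the sponsor.** No comparator is named for the relative difficulties in Hypothesis 2. If the reference scores came from first exposures, an unpractised baseline is the like-for-like comparison. A practice run before baseline could then bias Hypothesis 2 the other way, so none is proposed here.
- **A percentage inflation.** An assumed gain of 0.2 to 0.4 on an assumed true effect of 0.3 gives 0.2/0.3 = 67% to 0.4/0.3 = 133%. Both inputs are chosen, so the percentage says nothing about this trial.

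**Conclusion.** The point holds, with limited weight. As the plan is written, any practice gain on PAL, SWM and RVP enters the reported cognitive effect size in full and cannot be told apart from an effect of yoga, so the change does not support a statement about target engagement. This rests on three features of the document: one group, the same tests at both time points, and no described means of separating retest from treatment.

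The bias acts towards apparent improvement to the extent that practice raises scores. Its size is unknown, and a negligible practice effect at about 10 weeks is not ruled out. The probabilities above depend on assumed practice effects of 0.2 to 0.5 SD of change and a true yoga effect of zero; they show what a modest gain would do, not that one occurred. Feasibility endpoints and Hypothesis 2 are outside this finding.

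**What to change.** - **Statistical Plan and Data Analysis:** add that pre-post CANTAB change includes any retest effect, will not be attributed to yoga or counted as target engagement, and will not be used to size the next trial.
- **CANTAB paragraph, Study Assessments:** state which test versions are used. Specify a different stimulus version at post-treatment where the existing software provides one and testing is not already complete.
- **Table 1:** reconcile the CANTAB time points with the text, and the 1-12 week column heading with the 10-week programme. If the original table does mark baseline, no change to the CANTAB row is needed.

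The cost is a few sentences and, where available, a software setting; no visit or procedure is added. The downsides are that the cognitive change data will support a weaker conclusion, and that alternate versions may differ slightly in difficulty. An alternate version may reduce carry-over of specific items but need not remove familiarity with the task, so the reporting sentence is needed either way.
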